2.2.2. Secondary

The following efficacy parameters will be assessed:

- Physician global evaluation of disease activity at each visit.
- Number of joints with active arthritis at each visit.
- Number of joints with limitation of motion at each visit.
- Index of inflammation (C-reactive protein [CRP] and Erythrocyte Sedimentation Rate [ESR]) at each visit.
- Childhood Health Assessment Questionnaire (CHAQ) at each visit.
 - Parent's Assessment of Physical Function (CHAQ Disability Index).
 - Parent's Assessment of Child's Arthritis Pain (CHAQ Discomfort Index, Visual Analog Scale [VAS]).
 - Parent's Global Assessment of Overall Wellbeing (CHAQ subsection, Visual Analog Scale [VAS]).
- JIA American College of Rheumatology (ACR) response at each visit and occurrence of JIA ACR disease flare after Month 3.
- JIA ACR Clinical Inactive Disease status and Clinical Remission on Medication at each visit.
- Change from baseline in Juvenile Arthritis Disease Activity Score (JADAS) 27- CRP and JADAS 27-ESR, and occurrence of JADAS minimum disease activity and inactive disease at each visit.
- Eligibility of tapering defined per protocol for corticosteroids, MTX/leflunomide, and tofacitinib.
- In subjects with **sJIA**: "Absence of Fever", defined as absence of fever due to sJIA in the week preceding the assessment at each visit.

- In subjects with Enthesitis Related Arthritis (**ERA**): Change from baseline in the Tender Enteseal Assessment, Modified Schober's Test, Overall Back Pain and Nocturnal Back Pain responses at various visits.
- In subjects with psoriatic arthritis (**PsA**): Change from baseline in body surface area (BSA) affected by psoriasis and Physician's Global Assessment (PGA) of psoriasis) at various visits.

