#### **3.2. Secondary Endpoints**

The following efficacy parameters will be assessed:

- Change from baseline in physician global evaluation of disease activity at each visit.
- Change from baseline in number of joints with active arthritis at each visit.

- Change from baseline in number of joints with limitation of motion at each visit.
- Change from baseline in index of inflammation (C-reactive protein [CRP] and Erythrocyte Sedimentation Rate [ESR]) at each visit.
- Childhood Health Assessment Questionnaire (CHAQ) at each visit:
  - Change from baseline in Parent's Assessment of Physical Function (CHAQ Disability Index).
  - Change from baseline in Parent's Assessment of Child's Arthritis Pain (CHAQ Discomfort Index, Visual Analog Scale [VAS]).
  - Change from baseline in Parent's Global Assessment of Overall Wellbeing (CHAQ subsection, Visual Analog Scale [VAS]).
- JIA American College of Rheumatology (ACR) response at each visit.
- Occurrence of JIA ACR disease flare at each visit after Month 3.
- JIA ACR Clinical Inactive Disease status at each visit, and clinical remission at each visit after 24 weeks since study start. Note that clinical remission is counted as 6 months (24 weeks) of inactive disease during study, and 24 weeks will be used in programming.
- Change from baseline in Juvenile Arthritis Disease Activity Score (JADAS) 27 CRP and JADAS-27 ESR, and occurrence of JADAS minimum disease activity and inactive disease at each visit.
- Achieving eligibility of tapering for corticosteroids, methotrexate (MTX)/leflunomide, and tofacitinib, respectively.
- Achieving partial tapering success for corticosteroids, MTX/leflunomide, and tofacitinib, respectively.
- Achieving complete tapering success for corticosteroids, MTX/leflunomide, and tofacitinib, respectively.
- In subjects with sJIA: achieving "Absence of Fever", defined as absence of fever due to sJIA in the week preceding the assessment at each visit.
- In subjects with Enthesitis Related Arthritis (ERA): Change from baseline in the Tender Enthesial Assessment (TEA), Modified Schober's Test, Overall Back Pain and Nocturnal Back Pain responses at various visits.
- In subjects with psoriatic arthritis (PsA): Change from baseline in body surface area (BSA) affected by psoriasis and Physician's Global Assessment (PGA) of psoriasis at various visits.

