### 3.4. Baseline Variables

#### 3.4.1. Definition of Baseline

Baseline will be defined in the following way for all statistical analyses except for JIA ACR disease flare, and safety monitoring and discontinuation:

- First determine the number of off-study days (enrollment gap) between the last visit date in the qualifying study and the first visit date in this extension study.
- If the gap is  $\leq 14$  days, the baseline value will come from the baseline value of the qualifying study, if available. If it is not available, the baseline value will be missing.
- If the gap is  $> 14$  days, use the following decision tree to determine which baseline value, from the qualifying study or from this extension study, will be utilized in the analyses.

Qualifying Study Baseline Available [a]	Extension Study Baseline Available [b]	Baseline Value for Use in Analyses, if Gap $> 14$ days
No	No	No Baseline (Missing)
No	Yes	Extension Study
Yes	No	Qualifying study
Yes	Yes	Extension study

[a] The baseline values from the qualifying study with a randomized withdrawal design (i.e., A3921104 and A3921165) will come from the open-label period baseline.

[b] The baseline values from this extension study will come from 1) separate screening and baseline visits after EOS visit of the qualifying study, 2) a combined screening/baseline visit after EOS visit, or 3) a screening/baseline visit combined with the EOS visit. More specifically, extension study baseline will be the last non-missing assessment on or before Day 1 and prior to first dose of study drug administration in this extension study. Only data collected in the extension study database will be used. If a baseline value is not available by design (i.e., not planned to be collected at screening or baseline visit according to the protocol), extension study baseline availability will be “No” in the above decision tree.

For JIA ACR disease flare, baseline values will be from Month 3 visit of this extension study regardless of the gap calculated above.

For baseline definitions for use in safety monitoring and discontinuation, please see A3921145 protocol Appendix 8.

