## 5.3. Methods to Manage Missing Data

Missing data will not be imputed, and all analyses will be based on available data except Tanner Stage assessment and missing joint assessment. For Tanner Stage assessment, once a subject has reached the highest stage of development (Stage 5) then that score will be carried forward for the remainder of the study. More specifically, any missing Tanner Stage assessment after a Stage 5 score will be “imputed” with Stage 5, up to the next non-missing Tanner Stage assessment prior to study discontinuation. For missing joint assessment, the imputation method is provided in [Appendix 1.2](#)

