## 6.2. Secondary Endpoints

All efficacy endpoints are secondary and listed in [Section 3.2](#). [Table 2](#) summarizes the analysis sets to be used in the analysis of each efficacy endpoint.

The secondary efficacy endpoints will be summarized using descriptive statistics by visit for the binary and continuous endpoints respectively. The percent (for the binary endpoints) and mean change (for the continuous endpoints) over time and associated standard errors will be plotted for analyses in sJIA1, sJIA2 and pJIA analysis sets (see [Table 2](#)).

The binary endpoints are JIA ACR responses, occurrence of JIA ACR disease flare, JIA ACR clinical inactive disease status and clinical remission, occurrence of JADAS minimum disease activity and inactive disease, eligibility of tapering, partial tapering success and complete tapering success for corticosteroids, MTX/leflunomide, and tofacitinib, absence of fever for sJIA subjects at each visit. Number, frequency, percent and the associated standard error will be presented for binary variables. JIA ACR disease flare will only be summarized for those who have reached Month 3 Visit of this extension study.

The continuous endpoints are change from baseline in physician global evaluation of disease activity, number of joints with active arthritis, number of joints with limitation of motion, CRP, ESR, CHAQ, JADAS-27 CRP, JADAS-27 ESR at each visit. Number, mean, standard deviation, standard error of the mean, median, quartiles, minimum, and maximum will be presented for continuous variables.

For ERA subjects, change from baseline in TEA, Modified Schober's Test, Overall Back Pain, Nocturnal Back Pain at each visit will be summarized as continuous variables.

For PsA subjects, change from baseline in BSA affected by psoriasis, PGA of psoriasis at each visit will be summarized as continuous variables.

For ESR and any efficacy endpoint summaries involving ESR, all ESR data points including those collected with expired/non-standard ESR kits will be used for analysis. Supportive analyses will be performed to evaluate the impact of expired/non-standard ESR kits (see Section 6.2.1).

For CHAQ and any efficacy endpoint summaries (i.e., JIA ACR responses, JIA ACR flare, and JADAS) involving CHAQ, subjects with invalid CHAQ measurements will be excluded for the visits where these invalid measurements were made. Examples of invalid CHAQ measurements include:

- incorrectly translated CHAQ data

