**Table 2. Analysis Sets for Each Efficacy Endpoint**

		sJIA1*	sJIA2*	pJIA*	ERA	PsA
Efficacy endpoints defined for all subjects						
	Change from baseline (CFB) in CRP and ESR	Y	Y	Y	Y	Y
	CFB in physician global evaluation of disease activity	Y	Y	Y	Y	Y
Joint assessment	CFB in number of joints with active arthritis	Y	Y	Y	Y	Y
	CFB in number of joints with limitation of motion	Y	Y	Y	Y	Y
CHAQ	CFB in CHAQ Disability Index	Y	Y	Y	Y	Y
	CFB in CHAQ Discomfort Index	Y	Y	Y	Y	Y
	CFB in CHAQ Parent's Global Assessment of Overall Wellbeing	Y	Y	Y	Y	Y
JIA ACR	JIA ACR 30/50/70/90/100 response	Y	Y	Y	Y	Y
	JIA ACR disease flare after Month 3	Y	Y	Y	Y	Y
	JIA ACR Clinical Inactive Disease	Y	Y	Y	Y	Y
	JIA ACR Clinical Remission	Y	Y	Y	Y	Y
JADAS-27 CRP & JADAS-27 ESR	Change from baseline	Y	Y	Y	Y	Y
	JADAS minimum disease activity	Y	Y	Y	Y	Y
	JADAS inactive disease	Y	Y	Y	Y	Y
Tapering for corticosteroids, MTX/leflunomide and tofacitinib, respectively	Achieving eligibility of tapering	Y	Y	Y	Y	Y
	Achieving partial tapering success	Y	Y	Y	Y	Y
	Achieving complete tapering success	Y	Y	Y	Y	Y
Efficacy endpoints defined for specific subtypes						
In subjects with sJIA	Achieving "Absence of Fever"	Y	Y	NA	NA	NA
In subjects with ERA	CFB in TEA	NA	NA	NA	Y	NA
	CFB in Modified Schober's Test	NA	NA	NA	Y	NA
	CFB in Overall Back Pain	NA	NA	NA	Y	NA
	CFB in Nocturnal Back Pain	NA	NA	NA	Y	NA
In subjects with PsA	CFB in BSA affected by psoriasis	NA	NA	NA	NA	Y
	CFB in PGA of psoriasis	NA	NA	NA	NA	Y

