#### Appendix 1.4. Disease Flare

JIA ACR flare (Brunner 2002) is defined as a worsening of 30% or more in 3 or more of the 6 variables of the JIA core set listed above, with no more than one variable improving by 30% or more. In addition, the following minimum worsening contingencies apply: if either the number of active joints or the number of joints with limited range of motion is included in the calculation of "flare" then there must be a worsening of at least two joints. If the Physician's or parent/legal guardian global rating scores are used in the definition of "flare" then there must be a worsening of at least 2 units on the 10-unit scales. If the ESR is used in the definition of "flare" then the second value for the ESR used in the calculation must be above the upper limit of normal for the ESR.

In addition, for subjects with sJIA from A3921104 and A3921165, a disease flare may also constitute a recurrence of fever due to sJIA of  $>38^{\circ}\text{C}/100.4^{\circ}\text{F}$  (oral) or  $>101.4^{\circ}\text{F}/38.6^{\circ}\text{C}$  (rectal) on 2 or more consecutive days (Ruperto 2012). Note that here is different from index study A3921104 protocol, where 2 or more consecutive days for fever was not required.

Missing component handling will be the same as that for JIA ACR responses (See [Appendix 1.3](#)).

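### The SAP reports JIA ACR flare only as a status at each visit, so no planned output shows how many subjects ever flare after Month 3; a per-subject summary would be a cheap improvement

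*SAP*

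**What the plan says.** Protocol 2.2.2 lists as one secondary endpoint "JIA American College of Rheumatology (ACR) response at each visit and occurrence of JIA ACR disease flare after Month 3". SAP 3.2 splits this bullet, and the flare part becomes "Occurrence of JIA ACR disease flare at each visit after Month 3".

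The derivation is made visit by visit. In SAP Appendix 1.4 the event "is defined as a worsening of 30% or more in 3 or more of the 6 variables of the JIA core set listed above". Minimum-worsening conditions and, for sJIA, a fever criterion are added. The reference is fixed in SAP 3.4.1: "For JIA ACR disease flare, baseline values will be from Month 3 visit of this extension study regardless of the gap calculated above".

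For analysis, SAP 6.2 states "The secondary efficacy endpoints will be summarized using descriptive statistics by visit for the binary and continuous endpoints respectively" and adds "JIA ACR disease flare will only be summarized for those who have reached Month 3 Visit of this extension study". Binary endpoints get number, frequency, percent and standard error. SAP Table 2 uses the shorter label "JIA ACR disease flare after Month 3" but attaches no other analysis to it. SAP 5.3 says "Missing data will not be imputed, and all analyses will be based on available data except Tanner Stage assessment and missing joint assessment".

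No section defines first flare, time to flare, or a count of subjects with at least one flare. The incidence rates in SAP 6.6 are for adverse events.

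**The concern.** The secondary objective is persistence of efficacy, and flare is the listed endpoint that most directly captures its loss. A by-visit flare percentage is a point prevalence. It answers how many of the subjects seen at a visit are in flare then, not how many have lost control at some time. Two routes take a subject who has flared out of later percentages:

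- **Recovery.** Protocol Appendix 3 permits adjustment of background therapy for worsening disease. A subject who flares, is adjusted and improves counts as a non-flarer from then on. In sJIA a flare can be a recurrence of fever on consecutive days, which is an episode rather than a lasting state.
- **Exit.** Without imputation, a subject who flares and leaves is absent from later numerators and denominators. Protocol 2.3.2 reports that insufficient clinical response was the most common reason for discontinuation at the 2019 interim cutoff. Protocol Appendix 13 (Belgian sites) makes a single flare a trigger for evaluating discontinuation.

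The index study A3921104 had flare occurrence by Week 44 as its primary endpoint (Protocol 2.3.2). The extension plans no per-subject flare figure of that form.

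**Working it through.** **Is there a stated figure to reproduce?** No. The documents give no flare rate, flare duration, power or sample size for flare. The figures below are illustrations on assumed rates, with complete follow-up.

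**Inputs.**
- Visit spacing (Protocol section 3): every 3 months after Month 3. Visits after Month 3 number k = 3 by Month 12 (Months 6, 9, 12), k = 7 by Month 24 and k = 19 by Month 60.
- By-visit flare percentage p: assumed constant at 5%, with 2% and 10% as alternatives.
- Mean flare duration d, in visits: assumed.

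**Case 1: independent one-visit flares.** Share ever flaring = 1 − (1 − p)^k. For p = 5% at Month 24: 1 − 0.95^7 = 30.2%.

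| p | Month 12 | Month 24 | Month 60 |
|---|---|---|---|
| 2% | 5.9% | 13.2% | 31.9% |
| 5% | 14.3% | 30.2% | 62.3% |
| 10% | 27.1% | 52.2% | 86.5% |

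**Case 2: same 5% at every visit, varying duration.** Use a two-state chain (in flare or not). A subject in flare recovers by the next visit with probability 1/d. To hold prevalence at p, a subject not in flare must enter flare with probability a = (p/d)/(1 − p). Then the share ever flaring = 1 − (1 − p)(1 − a)^(k−1).

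Worked example, d = 2 at Month 24: a = 0.025/0.95 = 0.0263, and 1 − 0.95 × 0.9737^6 = 19.0%.

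| Mean duration | Month 12 | Month 24 | Month 60 |
|---|---|---|---|
| 1 visit | 14.7% | 31.3% | 64.1% |
| 2 visits | 9.9% | 19.0% | 41.2% |
| 4 visits | 7.5% | 12.3% | 25.2% |
| Same subjects throughout (d = 1000) | 5.0% | 5.0% | 5.1% |

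Every row yields the same by-visit display, a flat 5%. The planned table therefore cannot distinguish about 5% from about 30% ever flaring by Month 24.

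**Effect of exits.** The tables assume that nobody leaves. If subjects leave after a flare, the by-visit percentage at later visits is taken over those who remain, so the display is further removed from the share who have ever flared.

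**The case against.** **Does the SAP contradict the protocol?** A reader might infer so, because Protocol 2.2.2 attaches the by-visit phrase to ACR response and gives flare only a start time. The documents do not support that reading firmly. The same list uses the word occurrence for JADAS states that are explicitly by visit. Protocol 9.2.2 plans by-visit summaries of the efficacy measures and makes no exception for flare. Because the flare reference is the Month 3 visit, the start time may only mark when flare can first be assessed. The protocol wording permits a per-subject endpoint without requiring one. This objection stands.

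**Is the understatement several-fold?** A reader might also infer a fixed multiplier, such as 5- to 10-fold. That needs short flares and about three years of follow-up. With independent one-visit flares at 5%, Month 36 (k = 11) gives 1 − 0.95^11 = 43.1%, a ratio of 43.1/5 = 8.6. At Month 12 the ratio is 14.3/5 = 2.9, and if flares persist it is close to 1. Status judged against a fixed Month 3 value is plausibly correlated across visits, so independence lies near one extreme. No multiplier can be claimed.

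**Is loss of control visible elsewhere?** In part. ACR response, inactive disease, JADAS and clinical remission are also reported, and SAP 6.6 gives rates for adverse events, including those leading to discontinuation. None of these counts subjects with an ACR flare.

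**Does it matter in a descriptive study?** No hypothesis is tested (SAP 5.1), so no error rate or decision rule is affected. Protocol 9.2.2 also allows exploratory analyses, though it commits to none for flare. Both points limit the weight of the concern. They do not supply the missing figure.

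**Conclusion.** The gap is real but modest. As written, the SAP produces no estimate of the share of subjects who ever flare after Month 3, and that share cannot be recovered from the by-visit percentages. Its size is unknown because the documents give neither flare rate nor duration. With an assumed constant 5% by visit and complete follow-up, the Month 24 share runs from about 5% to about 30%, depending only on how long flares last and whether the same subjects recur.

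This is a cheap improvement to how persistence of efficacy is reported. It is not an error against the protocol.

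**What to change.** Keep the by-visit flare table. Add to SAP 3.2 and 6.2, for each analysis set:

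1. The number and percent of subjects with at least one JIA ACR flare after Month 3, among those who reached the Month 3 visit.
2. The cumulative incidence of first flare from the Month 3 visit (Aalen-Johansen estimator), with exit without flare as a competing event and study closure as censoring. Report it at time points that follow-up supports: Month 12 for subjects from A3921165, whose follow-up may stop at about one year under the study-end rule, and later for the others.
3. The same display for a combined event of flare or discontinuation for insufficient clinical response. Such exits are themselves loss of efficacy, and treating them only as competing events would leave them outside the flare curve.

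The cost is SAP wording and one extra table or figure per analysis set. No new data are needed.

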### 3.3. Exploratory Endpoints

- Plasma concentration time data for tofacitinib will be analyzed to characterize the PK in this subject population. Exposure-response relationship will be explored for various efficacy and safety endpoints after long-term exposure of tofacitinib.

### 3.4. Baseline Variables

#### 3.4.1. Definition of Baseline

Baseline will be defined in the following way for all statistical analyses except for JIA ACR disease flare, and safety monitoring and discontinuation:

- First determine the number of off-study days (enrollment gap) between the last visit date in the qualifying study and the first visit date in this extension study.
- If the gap is  $\leq 14$  days, the baseline value will come from the baseline value of the qualifying study, if available. If it is not available, the baseline value will be missing.
- If the gap is  $> 14$  days, use the following decision tree to determine which baseline value, from the qualifying study or from this extension study, will be utilized in the analyses.

Qualifying Study Baseline Available [a]	Extension Study Baseline Available [b]	Baseline Value for Use in Analyses, if Gap $> 14$ days
No	No	No Baseline (Missing)
No	Yes	Extension Study
Yes	No	Qualifying study
Yes	Yes	Extension study

[a] The baseline values from the qualifying study with a randomized withdrawal design (i.e., A3921104 and A3921165) will come from the open-label period baseline.

[b] The baseline values from this extension study will come from 1) separate screening and baseline visits after EOS visit of the qualifying study, 2) a combined screening/baseline visit after EOS visit, or 3) a screening/baseline visit combined with the EOS visit. More specifically, extension study baseline will be the last non-missing assessment on or before Day 1 and prior to first dose of study drug administration in this extension study. Only data collected in the extension study database will be used. If a baseline value is not available by design (i.e., not planned to be collected at screening or baseline visit according to the protocol), extension study baseline availability will be “No” in the above decision tree.

For JIA ACR disease flare, baseline values will be from Month 3 visit of this extension study regardless of the gap calculated above.

For baseline definitions for use in safety monitoring and discontinuation, please see A3921145 protocol Appendix 8.

### **3.4.2. Baseline Disease Characteristics**

For details of baseline definition, please see Section [3.4.1](#).

- Baseline CHAQ Disability Index
- Baseline CHAQ Discomfort Index
- Baseline CHAQ Parent Assessment of Overall Well-Being
- Baseline JADAS-27 CRP and JADAS-27 ESR
- Baseline number (%) of subjects with JADAS-27 CRP/ESR inactive disease, minimal disease activity, low disease activity, moderate disease activity and high disease activity, respectively
- Baseline number of joints with active arthritis
- Baseline number of joints with limitation of motion
- Baseline number of swollen joints
- Baseline number of painful/tender joints
- Baseline physician global evaluation of disease activity
- Baseline duration of morning stiffness
- Baseline ESR
- Baseline CRP
- Baseline number (%) of subjects who were Rheumatoid Factor positive (RF+) and negative (RF-)
- Baseline number (%) of subjects who were Antinuclear Antibodies positive (ANA+) and negative (ANA-)
- In subjects with ERA: baseline Tender Entheseal Assessment (TEA), baseline Modified Schober's Test, baseline Overall Back Pain, and baseline Nocturnal Back Pain
- In subjects with PsA: baseline %BSA and baseline PGA of Psoriasis

- In subjects with sJIA: baseline number (%) of subjects with fever, rash, serositis, splenomegaly, hepatomegaly, or generalized lymphadenopathy

